### **2.4.4.3 Analyses of other efficacy endpoints**

The analysis of other endpoints (see [Section 2.1.3](#)) will be descriptive with no formal testing. Summary statistics at scheduled visits based on observed value will be provided by each treatment group. Graphical presentations will also be used to illustrate trends over time as appropriate.

The number (%) of patients who used rescue therapy will be summarized by treatment group during the core (see [Section 2.5.4](#)) and the entire double-blind treatment periods. A KM curve for the time to first rescue therapy will be provided by treatment group. A list of patients who used rescue therapy will also be provided (see [Section 2.5.4](#)).

### **2.4.4.4 Multiplicity issues**

To control the family-wise type I error, a fixed sequence testing procedure will be applied.

Once the primary hypothesis (superiority of the change from Baseline to Week 26 in HbA1c comparing sotagliflozin 400 mg versus placebo) is statistically significant for the primary efficacy endpoint at  $\alpha = 0.05$  (2-sided), the following secondary hypothesis based on change from Baseline scores will be tested in the following prioritized order:

1. Change from Baseline to Week 26 in FPG.
2. Change from Baseline to Week 26 in body weight.
3. Change from Baseline to Week 12 in SBP for patients with baseline SBP  $\geq 130$  mmHg.
4. Change from Baseline to Week 12 in SBP for all patients.
5. Proportion of patients with HbA1c  $< 7.0\%$  at Week 26.

If any hypothesis is found to be not statistically significant, the testing procedure will be stopped and the following hypotheses will not be tested.

No multiplicity adjustment will be made on other secondary efficacy variables than mentioned above.

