11.4.2 Analyses of efficacy endpoints

Efficacy analyses will be performed on the ITT population.

Statistical testing will be performed for primary endpoint and secondary endpoints at Week 26 (or Week 12 for SBP). All efficacy variables after Week 26 will only be summarized by descriptive statistics without formal statistical testing.

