11.4.2.4 Multiplicity considerations

To control the family-wise type I error, a fixed-sequence testing procedure will be applied.

Once the main study primary variable (change from Baseline to Week 26 in HbA1c) is statistically significant at $\alpha = 0.05$ (2-sided), a hierarchical testing procedure will be performed to test the following main study secondary efficacy variables by the following prioritized order. The testing will stop as soon as an endpoint is found to be not statistically significant at $\alpha = 0.05$ (2-sided):

- Change from Baseline to Week 26 in FPG

- Change from Baseline to Week 26 in body weight
- Change from Baseline to Week 12 in SBP for patients with Baseline SBP \geq 130 mmHg
- Change from Baseline to Week 12 in SBP for all patients
- Proportion of patients with HbA1c $<$ 7.0% at Week 26

No multiplicity adjustment will be made on other secondary efficacy variables than mentioned above.

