#### 2.1.3.2 Secondary efficacy endpoint(s)

- Change from Baseline to Week 26 in FPG.
- Change from Baseline to Week 26 in body weight.
- Change from Baseline to Week 12 in SBP for patients with baseline SBP  $\geq$ 130 mmHg.
- Change from Baseline to Week 12 in SBP for all patients.
- Proportion of patients with HbA1c <6.5%, <7.0% at Week 26.

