#### **2.4.4 Analyses of efficacy endpoints**

Efficacy analyses will be performed on the ITT population using the efficacy assessments collected during the study, including those obtained after IMP discontinuation or introduction of rescue therapy, unless otherwise specified.

Statistical testing will be performed for primary endpoint and some secondary endpoints at Week 26 (or Week 12 for SBP) as specified in following subsections. All efficacy variables after Week 26 will only be summarized by descriptive statistics without formal statistical testing.

Missing data for efficacy analyses is identified through steps described in [Section 2.5.4](#).

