#### **2.4.4.1 Analysis of primary efficacy endpoint**

The statistical test will be two-sided tests at a nominal 5% significance level.

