The categorical secondary efficacy variables of HbA1c  $< 6.5\%$ ,  $< 7\%$  at Week 26 will be analyzed respectively using a Cochran-Mantel-Haenszel (CMH) method stratified by randomization stratum of HbA1c ( $\leq 8.5\%$ ,  $> 8.5\%$ ), randomization stratum of metformin use at Screening (Yes, No), and randomization stratum of SBP ( $< 130$  mmHg,  $\geq 130$  mmHg). The proportion in each treatment group will be provided, as well as the difference of proportions between sotagliflozin 400 mg and placebo with the associated 2-sided 95% CI. For HbA1c responders at Week 26 ( $< 6.5\%$ ,  $< 7\%$  respectively), all values at Week 26 will be used to determine whether a patient is a responder or not, even if they are measured after IMP discontinuation or rescue medication use. Patients who have no HbA1c measurement at Week 26 will be treated as non-responders. Summary tables and graphs will also be provided by treatment group at scheduled visits.

For between-group comparison, a sensitivity analysis will be performed respectively for HbA1c  $< 6.5\%$  responder analysis by excluding patients whose HbA1c values at baseline are  $< 6.5\%$ , and for HbA1c  $< 7\%$  responder analysis by excluding patients whose HbA1c values at baseline are  $< 7\%$  using the same CMH test mentioned above. Similarly, by-visit summary may also be provided excluding those patients.

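### HbA1c <6.5% is the only named secondary efficacy endpoint outside the fixed sequence; adding it as the last step would make a controlled claim possible at no cost to the other tests.

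*SAP*

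**What the plan says.** The secondary efficacy list in SAP 2.1.3.2 has five bullets but six variables, because the last bullet holds two responder thresholds: "Proportion of patients with HbA1c <6.5%, <7.0% at Week 26". The same pair appears among the secondary objectives (Protocol 5.2, SAP 1.2.2) and in Protocol 9.1.2.

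Both thresholds get a CMH comparison stratified by the three randomization factors, with a difference in proportions and a two-sided 95% CI (Protocol 11.4.2.2, SAP 2.4.4.2). SAP Appendix C lists this as the primary analysis for both. SAP 2.4.4.2 adds a sensitivity comparison for each threshold, "using the same CMH test mentioned above".

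On which endpoints are formally tested, Protocol 11.4.2 says: "Statistical testing will be performed for primary endpoint and secondary endpoints at Week 26 (or Week 12 for SBP"). SAP 2.4.4 is narrower: "Statistical testing will be performed for primary endpoint and some secondary endpoints at Week 26", as set out in its later subsections.

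On multiplicity, SAP 2.4.4.4 begins: "To control the family-wise type I error, a fixed sequence testing procedure will be applied". The order is HbA1c change, FPG, body weight, SBP in patients with baseline SBP ≥130 mmHg, SBP in all patients, then HbA1c <7.0%. Testing stops at the first non-significant result. Protocol 11.4.2.4 has the same order and also ends at <7.0%. Both then state: "No multiplicity adjustment will be made on other secondary efficacy variables than mentioned above". Neither gives a reason for separating <6.5% from <7.0%.

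**The concern.** One of six named secondary efficacy variables has a between-group test but no place in the testing order. Nothing makes its p-value depend on the earlier steps, or even on the primary. Nor is it labelled nominal or descriptive, although the plan uses such a label elsewhere: the other efficacy endpoints are declared descriptive without formal testing (Protocol 11.4.2.3, SAP 2.4.4.3). A <6.5% p-value could therefore appear in the report beside controlled secondary results and be read as having the same standing.

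Two things are at stake. A positive result on a named secondary objective cannot be claimed with error control. And a reader who treats it as confirmatory accepts more than 5% error over the full set of named efficacy hypotheses. In a fixed sequence both can be avoided without taking anything from the endpoints already in it.

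**Working it through.** **1. The plan's own figure.** Inputs from Protocol 11.1 and SAP 1.3: 250 per arm, difference 0.6%, SD 1.2%, two-sided alpha 0.05. The standard error is 1.2 × √(2/250) = 0.1073, so 0.6/0.1073 = 5.59 and power = Φ(5.59 − 1.96) = Φ(3.63) = 0.9999. This agrees with the stated 99% (SAP) and at least 99% (Protocol). It does not depend on where <6.5% stands.

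**2. What is left outside.** Setting SAP 2.1.3.2 against SAP 2.4.4.4, FPG, weight, both SBP analyses and <7.0% are matched. Only <6.5% remains.

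**3. Error for the six sequenced tests.** In a fixed sequence a false rejection requires the first true null hypothesis in the order to be rejected, and that is tested at 0.05. The six are therefore controlled at 0.05 whatever happens to <6.5%.

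**4. Error if <6.5% is counted as a seventh confirmatory test outside the sequence.** At most two tests then matter: the first true null in the sequence and <6.5%, each at 0.05. If they are independent, the chance of at least one false rejection is 1 − (1 − 0.05)² = 0.0975. For two-sided tests on jointly normal statistics, correlation can only lower this.

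**5. Effect of correlation.** The documents give no correlations, so these are assumptions: HbA1c with FPG 0.6, with <7.0% 0.7, with <6.5% 0.55; <7.0% with <6.5% 0.55; FPG with <7.0% 0.4, with <6.5% 0.35; the two SBP tests 0.75; weight with the glycemic endpoints 0.1; SBP with all others 0.05. One million simulated sets of seven two-sided z-tests, with a large effect wherever the null is false, gave these probabilities of at least one false rejection:

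| True nulls | <6.5% outside (as planned) | <6.5% tested only if primary is significant | <6.5% as last step |
|---|---|---|---|
| All seven | 0.089 | 0.050 | 0.050 |
| <6.5% only | 0.050 | 0.050 | 0.050 |
| FPG and <6.5% | 0.094 | 0.094 | 0.050 |
| Weight and <6.5% | 0.097 | 0.097 | 0.050 |
| Both SBP tests and <6.5% | 0.097 | 0.097 | 0.050 |
| <7.0% and <6.5% | 0.090 | 0.090 | 0.050 |

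Under independence the first column was 0.097 to 0.098 whenever a sequenced test was also null, matching 0.0975 within simulation error. A separate patient-level simulation (6,000 null trials of 500 patients, ANCOVA on HbA1c change and a stratified Mantel-Haenszel test on <6.5%) gave rejection rates of 0.046 and 0.046, and 0.0845 for either. It needs an assumed responder rate, which the documents do not supply, so it marks only the lower end of the range.

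**6. Cost to the earlier tests.** Rejections at the first six tests were identical in every replicate with <6.5% outside or last. Requiring only a significant primary is not enough, as the third column shows.

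**7. Cost to <6.5% itself.** As the last step it is reached only if all six earlier tests succeed. Suppose the five secondary tests were independent with equal power q (an assumption) and the primary had power 0.9999. The probability of reaching step 6 is then q⁵ × 0.9999: 0.33 for q = 0.80, 0.59 for q = 0.90, 0.77 for q = 0.95.

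**The case against.** The strongest reply is that this is a deliberate and open choice. Both documents fix the same order and both say that anything outside it is unadjusted, so the plan promises no controlled conclusion for <6.5%. One threshold may reasonably represent the responder bullet while the stricter, nested one is supportive. The word some in SAP 2.4.4 can be read as describing exactly this exclusion, and an estimate with a CI is not a claim. All of this stands. It shows that the plan contains no hidden inflation.

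A reader might infer that the stated family-wise control is broken, or that the trial's error rate is simply 8.5% instead of 5%. The documents support neither. The control statement is followed by the list it covers and by an explicit exception, and the covered tests stay at 5%. The excess arises only if the family is widened to include a test that the plan puts outside it, and its size depends on assumed correlations.

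The reply does not settle the status of <6.5%. Protocol 11.4.2 has no such limiting word, the SAP subsection that specifies the analyses gives <6.5% a CMH test, and nothing labels it nominal. It also remains true that adding the endpoint last is free only for the other tests; step 7 of the working shows what the <6.5% claim itself would depend on.

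**Conclusion.** The point holds as an available improvement, not as an error. The plan is valid at 5% for the primary and the five sequenced secondary tests. The seventh named efficacy hypothesis cannot support a controlled claim as written, although it could be given one without loss elsewhere.

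If <6.5% were also read as confirmatory, error over all seven would be about 8.5% to 9.7% when at least one sequenced hypothesis is also null. The 9.75% ceiling assumes two-sided tests on jointly normal statistics. If <6.5% is the only true null, the error is 5% either way. The point covers secondary efficacy endpoints only; the secondary safety objective is descriptive, with no testing planned (SAP 2.4.5).

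**What to change.** Before unblinding, add the proportion of patients with HbA1c below 6.5% at Week 26 as step 6, after <7.0%, in SAP 2.4.4.4 and Protocol 11.4.2.4. State that if the sequence stops earlier, the <6.5% estimate and CI are reported as nominal.

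The statistical cost to the primary and the first five secondary tests is nil. The text change is one line in each document, plus the nominal-reporting sentence. The Protocol line is an amendment and carries the review steps of Protocol section 15; the last change to the testing order was likewise made by protocol amendment (SAP 1.5, Table 1).

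If the sponsor prefers to leave the order alone, labelling <6.5% as nominal in both documents would remove the ambiguity, but it would not make a controlled claim possible.

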### **2.4.5 Analyses of safety data**

The summary of safety results will be presented by treatment group.

Safety endpoints are presented in [Section 2.1.4](#). The summary of safety results will be presented by treatment group. The safety data will be summarized for the 26-week core treatment period and the 79-week entire treatment period separately, unless otherwise specified.

The “observation period” defined in [Section 2.1.4](#) is applicable in all safety analyses for the classification of AEs, determination of treatment-emergent PCSA values and the last on-treatment value for the laboratory, vital sign and ECG.

### **General common rules**

All safety analyses will be performed on the safety population as defined in [Section 2.3.2](#), unless otherwise specified, using the following common rules:

- Safety data in patients who do not belong to the safety population (eg, exposed but not randomized) will be listed separately.
- The baseline value (with the exception of serum creatinine and eGFR) is defined as the last available value before the first dose of double-blind IMP, with the exception of creatinine and eGFR, where the baseline value is defined as the average of all values before the first dose of double-blind IMP.
- PCSA values are defined as abnormal values considered medically important by the Sponsor according to predefined criteria/thresholds based on literature review and defined by the Sponsor for clinical laboratory tests, vital signs, and ECG ([Appendix A](#)).
- PCSA criteria will determine which patients had at least 1 PCSA during the TEAE period, taking into account all evaluations performed during the TEAE period, including nonscheduled or repeated evaluations. The number of all such patients will be the numerator for the treatment-emergent PCSA percentage.
- The treatment-emergent PCSA denominator by group for a given parameter will be based on the number of patients assessed for that given parameter during the TEAE period by treatment group in the safety population.
- For laboratory parameters cited in the protocol as efficacy endpoints (including HbA1c and plasma glucose etc.), PCSA summaries will not be provided. These parameters will be summarized in efficacy [Section 2.4.4](#). For creatinine and eGFR, PCSA summaries will be presented in safety [Section 2.4.5](#) while descriptive summaries in efficacy [Section 2.4.4](#).
- For quantitative safety parameters based on central laboratory/reading measurements, descriptive statistics will be used to summarize results and change from baseline values by visit and treatment group for the 79-week entire treatment period only. Summaries will include the last on-treatment value. The last on-treatment value is commonly defined as the value collected at the same day/time of the last administration of IMP for the 79-week entire treatment period. If this value is missing, this last on-treatment value will be the closest value prior to the last administration of IMP during the 79-week entire treatment period.
- The analysis of the safety variables will be essentially descriptive and no statistical testing is planned. Relative risks versus placebo and their 95% CIs may be provided, if relevant.
- Selected safety analyses will be summarized by age, gender, racial subgroups, and other pertinent subgroups (see details in [Section 2.4.5.1](#) and [Section 2.4.5.2](#)).

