8.2.2 Rescue therapy

The threshold values are defined as follows, depending on study period:

- FPG >270 mg/dL (15.0 mmol/L) from Randomization up through the scheduled Week 8 Visit
- FPG >240 mg/dL (13.3 mmol/L) after the Week 8 visit up through the scheduled Week 12 Visit
- FPG >200 mg/dL (11.1 mmol/L) after the Week 12 Visit through the end of the 26-week Core Treatment Period
- FPG >170 mg/dL (9.4 mmol/L) or HbA1c \geq 8.0% after the Week 26 Visit through the end of the treatment period (Week 79)

Routine fasting SMBG (see [Section 9.2.1.6](#)) and central laboratory alerts on FPG (and HbA1c at Week 26 and onward) are set up to ensure that glycemic parameter results remain under predefined thresholds.

- If one fasting SMBG value exceeds the specific glycemic limit on one day, the patient checks it again during the two following days. If all the values in three consecutive days exceed the specific limit, the patient should contact the Investigator and a central laboratory FPG measurement (and HbA1c at Week 26 and onward) be performed as soon as possible, preferably within 7 days, to confirm the hyperglycemia
- Upon receipt of a central laboratory rescue alert, a central laboratory re-test **must** be completed and confirmed as exceeding the threshold for rescue before rescue therapy is initiated. The re-test confirmation should be performed as soon as possible, but within 7 days of receipt, by unscheduled visit

In the event that a confirmatory FPG and/or HbA1c exceeds the threshold, the Investigator should ensure that no reasonable explanation exists for insufficient glucose control and in particular that:

- The increased FPG has been tested at a fasting status (ie, no food intake for \geq 8 hours)
- Investigational medicinal product is given at the planned dose
- There is no intercurrent disease, which may jeopardize glycemic control (eg, infectious disease)
- Compliance to treatment is appropriate
- Compliance to diet and lifestyle is appropriate

If any of the above can reasonably explain the insufficient glycemic control, the Investigator should consider not initiating rescue medication and should undertake appropriate action, ie:

- Assess plasma glucose in fasting condition (ie, after at least 8 hours fast)
- Initiate an evaluation and treatment of intercurrent disease (to be reported in AE/concomitant medication parts of the e-CRF and the medical record)
- Stress the absolute need to be compliant with treatment

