8.3 BLINDING PROCEDURES

8.3.1 Methods of blinding

To maintain blinding, sotagliflozin and placebo tablets and packaging will be blinded and indistinguishable.

During the double-blind treatment period each treatment package will be labeled with a number, which is generated by a computer program from Sanofi. Investigators will not have access to the randomization (treatment) code except under circumstances described in [Section 8.3.2](#).

The randomization and the treatment allocation will be performed centrally by an IRT. The study biostatistician provides the randomization scheme to the IRT. Then, the IRT generates the patient randomization list from which it allocates treatment arms to the patients.

Fasting glucose (plasma or serum) and HbA1c will be masked to study sites and patients after randomization and until study end. To prevent partial unblinding, the central laboratory urine dipstick will not include the measurement of urine glucose.

The CEC members will perform adjudication in a blinded manner.

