11.4.3.5 Analyses of laboratory variables

The number and percentage of patients with PCSA or by the pre-defined categories (if no PCSA criterion is defined) at any evaluation during the on-treatment period will be summarized for each clinical laboratory test within each treatment group. The summaries will include patients in the safety population who have at least one laboratory test performed during the on-treatment period and, when required by the definition of the abnormality, with an available Baseline value and available laboratory normal ranges.

Descriptive statistics will be used to summarize the laboratory results and the changes from Baseline by visit and for the last on-treatment value within each treatment group. Shift tables and other tabular and graphical methods may be used to present the results for laboratory tests of interest. Listings will be provided with flags indicating the out of laboratory range values as well as the PCSA values.

Liver function tests, namely ALT, AST, alkaline phosphatase, and total bilirubin, are used to assess possible drug-induced liver toxicity. The proportion of patients with PCSA values at any post-Baseline visit by Baseline status will be displayed by treatment group for each parameter.

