#### **2.1.4.1 Hypoglycemia**

Hypoglycemia will be identified as events recorded on the dedicated e-CRF “Hypoglycemic event information” page, and will be categorized as follows (see study protocol for further details):

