#### 2.1.4.4 Laboratory safety variables

Clinical laboratory data consists of blood analysis (including hematology, clinical chemistry, amylase, lipase and lipid profile) and urinalysis. Clinical laboratory values will be summarized in both standard international units and conventional units when applicable.

Blood samples for clinical laboratories will be collected at designated visits (see study flowchart in [D](#)). The following laboratory data will be measured at a central laboratory:

- Hematology
  - Red blood cells and platelets: hemoglobin, hematocrit, red blood cell, platelets count,
  - White blood cells: white blood cell, neutrophils, lymphocytes, monocytes, basophils, eosinophils.
- Clinical chemistry
  - Metabolism: glucose (serum), creatine phosphokinase (CPK),
  - Electrolytes and minerals: sodium, potassium, chloride, bicarbonate (ie, carbon dioxide), calcium, phosphorus, magnesium,
  - Renal function: blood urea nitrogen (BUN), creatinine, uric acid,
  - Liver function: total protein, albumin, ALT, aspartate aminotransferase (AST), alkaline phosphatase (ALP), total bilirubin, Lactic acid dehydrogenase (LDH).
- Lipid parameters (fasting): total cholesterol (TC), high density lipoprotein cholesterol (HDL-C), low density lipoprotein cholesterol (LDL-C) (calculated by Friedwald equation, See [Section 2.5.1](#)), Non-HDL-C (calculated as the difference between TC and HDL-C), triglycerides (TG).
- Pancreatic enzymes: lipase, amylase.

Urine samples will be collected at designated visits (see study flowchart in [D](#)). The following laboratory data will be measured at a central laboratory:

- Urine dipstick includes: specific gravity, pH, protein, blood, ketones, bilirubin, urobilinogen, nitrite, and leukocyte esterase.
- Urine microscopy includes, but is not limited to: detection of formed cellular elements, casts, bacteria, yeast, parasites, and crystals in centrifuged urine sediment.

Serum glucose will be presented as efficacy parameters in [Section 2.4.4](#). For creatinine and calculated eGFR, Potentially Clinically Significant Abnormality (PCSA) summaries will be presented in the safety section while descriptive summaries in the efficacy section.

Technical formulas are described in [Section 2.5.1](#).

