**CRITERIA for POTENTIALLY CLINICALLY SIGNIFICANT ABNORMALITIES**  
**for phase 2/3 studies (oncology excepted)**  
**(From BTD-009536 May 21, 2014)**

Parameter	PCSA	Comments
	>10 ULN	Am J Cardiol April 2006. Categories are cumulative. First row is mandatory. Rows following one mentioning zero can be deleted.
CLcr (mL/min) (Estimated creatinine clearance based on the Cockcroft-Gault equation)	<15 (end stage renal disease) ≥15 - <30 (severe decrease in GFR) ≥30 - < 60 (moderate decrease in GFR) ≥60 - <90 (mild decrease in GFR) ≥ 90 (normal GFR)	FDA draft Guidance 2010 Pharmacokinetics in patients with impaired renal function-study design, data analysis, and impact on dosing and labeling
eGFR (mL/min/1.73m  ) (Estimate of GFR based on an MDRD equation)	<15 (end stage renal disease) ≥15 - <30 (severe decrease in GFR) ≥30 - < 60 (moderate decrease in GFR) ≥60 - <90 (mild decrease in GFR) ≥ 90 (normal GFR)	FDA draft Guidance 2010 Pharmacokinetics in patients with impaired renal function-study design, data analysis, and impact on dosing and labeling
Creatinine	≥150 µmol/L (Adults) ≥30% change from baseline ≥100% change from baseline	Benichou C., 1994.
Uric Acid Hyperuricemia Hypouricemia	>408 µmol/L <120 µmol/L	Harrison- Principles of internal Medicine 17 th Ed., 2008.
Blood Urea Nitrogen	≥17 mmol/L	
Chloride	<80 mmol/L >115 mmol/L	
Sodium	≤129 mmol/L ≥160 mmol/L	
Potassium	<3 mmol/L ≥5.5 mmol/L	FDA Feb 2005.
Total Cholesterol	≥7.74 mmol/L	Threshold for therapeutic intervention.
Triglycerides	≥4.6 mmol/L	Threshold for therapeutic intervention.
Lipasemia	≥3 ULN	
Amylasemia	≥3 ULN	
Glucose Hypoglycaemia Hyperglycaemia	≤3.9 mmol/L and <LLN ≥11.1 mmol/L (unfasted); ≥7 mmol/L (fasted)	ADA May 2005. ADA Jan 2008.

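### Serum glucose is a protocol safety parameter, but the SAP gives it no PCSA count, so low central-laboratory values are not tabulated by arm

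*SAP*

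**What the plan says.** **Protocol.** Table 2 in Section 9.2.1.3 includes serum glucose among the blood safety parameters measured centrally. Section 11.4.3 leaves out of the PCSA analysis only those parameters that the protocol does not cite as safety parameters. Section 11.4.3.5 then plans, for each clinical laboratory test and treatment group: "The number and percentage of patients with PCSA or by the pre-defined categories (if no PCSA criterion is defined) at any evaluation" in the on-treatment period.

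**SAP.** Section 2.1.4.4 lists serum glucose under clinical chemistry, then states "Serum glucose will be presented as efficacy parameters in" Section 2.4.4. The general common rules in Section 2.4.5 add: "For laboratory parameters cited in the protocol as efficacy endpoints (including HbA1c and plasma glucose etc.), PCSA summaries will not be provided". The same bullet treats two other parameters differently: "For creatinine and eGFR, PCSA summaries will be presented in safety" Section 2.4.5, with their descriptive summaries kept in the efficacy section. Appendix A carries a hypoglycemia criterion for glucose, "≤3.9 mmol/L and <LLN".

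**Hypoglycemia data.** SAP 2.1.4.1 takes these from a page that the site completes: "Hypoglycemia will be identified as events recorded on the dedicated e-CRF". Protocol 8.3.1 keeps the central values from the site: "Fasting glucose (plasma or serum) and HbA1c will be masked to study sites and patients after randomization and until study end".

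**The concern.** The two documents apply opposite tests. The protocol drops a parameter from the PCSA tables if it is not a safety parameter. The SAP drops it if it is an efficacy parameter. Serum glucose is a safety parameter by the first test and is treated as an efficacy parameter by the second, so a planned safety table disappears.

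This matters because Protocol 4.2 names hypoglycemia as a potential added risk when the drug is combined with an insulin secretagogue, and all patients here take a sulfonylurea. The central assay is run at the same scheduled visits in both arms. Sites cannot see its results, so a low central value cannot itself prompt an entry on the hypoglycemia page. A by-visit summary with mean, SD and minimum shows whether any value was low, but not how many patients had one.

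**Working it through.** The plan states no figure on this point, so the check is a comparison of texts followed by a count of scheduled measurements.

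**1. Which glucose measure is in conflict?**

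| | Chemistry-panel serum glucose | Fasting plasma glucose (FPG) |
|---|---|---|
| In Protocol Table 2 (safety) | Yes | No |
| Efficacy endpoint in Protocol 9.1 | No | Yes |
| PCSA count planned by Protocol 11.4.3 and 11.4.3.5 | Yes | No |
| PCSA count in the SAP | None, through 2.1.4.4 read with 2.4.5 | None, through 2.4.5 |
| Conflict | Yes | No |

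The conflict is confined to serum glucose. The 2.4.5 sentence alone does not create it, because that sentence covers parameters that the protocol cites as efficacy endpoints. The reassignment in 2.1.4.4 is what removes serum glucose.

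**2. Where does serum glucose go?** SAP 2.1.4.4 sends it to Section 2.4.4, but neither the endpoint lists in 2.1.3 nor Appendix C names it. SAP 2.4.5.4, meanwhile, describes PCSA incidence for each laboratory test grouped as in 2.1.4.4, and gives a normal-range table to tests without a criterion. Taken literally, that still covers serum glucose. The more specific statements in 2.1.4.4 and 2.4.5 say otherwise.

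**3. How many central values are scheduled?** From the flow chart, after baseline:
- FPG at Weeks 4, 12, 18, 26, 39, 52, 65 and 79: 8 per patient, at most 8 × 500 = 4,000.
- Serum glucose at Weeks 12, 26, 39, 52, 65 and 79: 6 per patient, at most 6 × 500 = 3,000.

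These are ceilings that assume all 500 patients attend every visit. They count samples, not low values.

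**4. What else captures low glucose?** Protocol 9.2.1.6 asks for fasting SMBG at least three times a week, including every on-site visit day. After Week 26 it may fall to once a week if readings stay below 120 mg/dL.
- No reduction: 3 × 79 = 237 readings.
- Full permitted reduction: 3 × 26 + 1 × 53 = 131 readings.
- Per scheduled FPG sample: 131 / 8 = 16.4 to 237 / 8 = 29.6.

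Every central draw falls on a day with an unmasked fasting SMBG. Readings of 70 mg/dL (3.9 mmol/L) or less go in the diary, which is reviewed on site. A measured value at or below that level without symptoms is an event category of its own (asymptomatic hypoglycemia).

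**5. What is left uncounted?** If L is the number of low central values and m the share with a matching e-CRF event, the uncounted number is L × (1 − m). The documents give neither L nor m, so no number can be put on it.

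**The case against.** The strongest reply is that hypoglycemia capture is already dense. SMBG outnumbers central sampling by at least 16 to 1, does not depend on symptoms, and feeds by-arm counts and rates of any hypoglycemia (SAP 2.4.5.1). SAP 2.1.4.1 also plans a separate look at <3.0 mmol/L. FPG minima by visit are reported, and the DMC may review other relevant safety data. Appendix A is a generic sponsor list with criteria this trial cannot use, such as QTc limits when the ECG is recorded only as normal or abnormal. A glucose entry there does not prove that a table was ever intended.

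Most of this stands, and it rules out three stronger readings that a reader might infer:
- **That a low central value can be neither acted on nor counted.** The paired visit-day SMBG can be seen, recorded and counted.
- **That the comparison rests on self-report alone.** It rests largely on scheduled meter readings.
- **That nobody is told of a low central value.** Protocol 8.2.2 says its SMBG checks and central alerts "are set up to ensure that glycemic parameter results remain under predefined thresholds", but that is the section on rescue for hyperglycemia. Its silence on low values shows nothing either way, and the laboratory manual and DMC charter are not among these documents.

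A reader might also apply an assumed rate of low values to the 4,000 FPG samples. That would use the measure that is not in conflict, with an unsupported rate, and would ignore lows already matched by an SMBG event.

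The reply does not remove the inconsistency. The protocol planned this count whatever Appendix A was written for. The SMBG route also passes through the investigator's judgment, since Protocol 10.6.1 asks that false or redundant low readings not be recorded as asymptomatic events. SAP 2.4.5.1 identifies asymptomatic events only by a flag in a listing, with no by-arm table of their own.

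**Conclusion.** The point holds as a limited inconsistency between protocol and SAP. Serum glucose is a cited safety parameter, PCSA counts are planned for it, and the SAP provides none, while handling creatinine and eGFR both ways. The practical loss is confined to low central values whose same-day SMBG is higher, missing or not entered on the e-CRF page. Its frequency is unknown.

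Nothing here touches the primary analysis, the sample size or the type I error. Some rows of the SAP change log are blacked out, so it cannot be said that the change was made without explanation. The conclusion assumes that the specific wording of SAP 2.1.4.4 and 2.4.5 overrides the general wording of 2.4.5.4. If it does not, the SAP contradicts itself and needs the same correction. The change is worth making because it restores a planned by-arm safety count at little cost.

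**What to change.** Amend SAP 2.1.4.4 and 2.4.5 so that glucose is handled like creatinine and eGFR, and bring both into line with SAP 2.4.5.4 and Protocol Table 2, 11.4.3 and 11.4.3.5:
- Keep the efficacy summaries as they are.
- Add one table by arm over the TEAE period: number (%) of patients meeting the Appendix A low-glucose criterion on central serum glucose, and number (%) with a value <3.0 mmol/L, the trial's own second threshold. The denominator is patients with at least one such measurement in that period, as SAP 2.4.5 already defines.
- Show FPG in the same table as a useful addition. The protocol does not require it.
- Add one listing of the low central values that states, for each, whether a matching e-CRF hypoglycemia event exists. This would supply the match rate that is missing now.

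The cost is one table and one listing from data already collected, with no new samples and no unmasking during the trial.
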